6.4.3 Risk Mitigation

Appropriate measures have been outlined in the study protocol to minimize the risk to subjects, while still providing the possible benefits of the treatment options to be studied. Although cardiac IRE ablation procedures pose potential risks, the criteria for subject selection, methods, personnel, facilities, and training that have been specified for this study are intended to minimize the risk to subjects undergoing this procedure.

Robust testing of the investigational devices at the component and the system level, within simulated clinical conditions, was successful with no adverse events identified.

The criteria for subject selection, methods, personnel, facilities, and training that are specified in this study are intended to minimize the risk to subjects undergoing this procedure.

Subjects will be screened carefully prior to enrollment in the study to ensure compliance with the inclusion and exclusion criteria. The exclusion criteria have been developed to eliminate confounding comorbidities that might interfere with study interpretation and exclude subjects with a medical history or condition that increases their risk of adverse events.

Subjects will be evaluated for the presence of left atrial thrombus prior to the procedure which is intended to decrease the potential for thromboembolic complications.

Participating investigators will be experienced and highly skilled in performing electrophysiology studies, intracardiac mapping and ablation of cardiac arrhythmias with other ablation catheters. Before this clinical study, investigators will undergo device training prior to performing study ablation procedures and in accordance with the physician training charter. Investigators will be trained on efficient maneuvering of IRE catheters and lesion creation on the sites similar to the target sites in human. Each site's Investigator will have satisfied the established training criteria. Procedures will be performed in electrophysiology laboratories with the assistance of skilled nurses and technicians. The laboratory will contain sufficient resuscitative equipment and facilities to manage any potential complications. Immediate access to cardiac surgical facilities, as well as a qualified cardiovascular surgeon, will be available during the ablation procedure in the event that surgical intervention becomes necessary.

The risk of PNP will be minimized by monitoring the PN with pacing maneuvers before and during the ablation of the right sided PVs. Investigators are encouraged to ensure diaphragmatic capture prior to and post ablation when in the region of the RSPV.

Optimal anti-coagulation prior to procedure, using Heparin to achieve an activated clotting time (ACT) of 350 seconds, during procedure and anticoagulation therapy for 2 months post procedure, can substantially decrease the risk of thrombus formation. Continuous irrigation of the catheter per IFU should reduce the risk.

The risk of ACE will be minimized by implementing an anti-coagulation regimen procedure and during procedure to avoid thrombi/emboli during procedure. Investigators will be instructed to minimize catheter exchange during procedure to mitigate the risk of air introduction. A single transseptal technique is recommended, with administration of heparin bolus prior to transseptal puncture.

To prevent effusion and tamponade, the VARIPULSE™ Catheter should be used as instructed, including ensuring that the loop of the catheter is not turned in a counterclockwise manner while inside of the patient.

To prevent the risk of pulmonary injury, investigators will be instructed to follow the recommended workflow.

To reduce the incidence of heart block the investigators are instructed to follow the recommended workflow.

In accordance with the 2020 ESC AF Management Guidelines[35], all subjects should be maintained on systemic oral anticoagulation therapy for at least two months post-procedure. In addition, the study protocol requires subjects to be on uninterrupted anticoagulation prior to the procedure. After two months post-procedure, a decision regarding continuation of systemic anti-coagulation agents will be based on the subject's risk for thromboembolism.

Finally, safety data will be evaluated periodically by a Data Monitoring Committee (DMC) as described in the DMC Charter. A Clinical Events Committee (CEC) will be implemented to adjudicate the primary safety endpoint events. The CEC will operate as described in the CEC Charter.

6.4.3 Precautions

Invasive electrophysiological evaluation and catheter ablation may impart some degree of risk to the subject. The risk of serious complications is generally related to the severity of cardiac disease. The degree of risk of the electrophysiological and catheter ablation procedures versus the potential benefit of the treatment of a cardiac arrhythmia should be determined by a qualified physician. Cardiac catheterization and electrophysiological procedures should be performed by qualified and appropriately trained personnel in an electrophysiology laboratory. The laboratory should contain sufficient resuscitative equipment and facilities to manage most potential complications. Failure to observe the contraindications, warnings, and precautions in these instructions and the instruction for use (IFU) may result in procedural complications. Immediate risks from ablation treatment may include: cardiovascular injury or perforation with or without cardiac tamponade, pulmonary embolus, tricuspid regurgitation, myocardial infarction, bleeding at the catheter insertion site, sepsis, and death.

Contraindications for catheter ablation of arrhythmia include: existing hemodynamic instability, bacteremia, coagulopathy, prosthetic tricuspid valve, intra-atrial or venous thrombosis, and pregnancy.

6.4.4 Known Potential Benefits

[figure not shown]
The treatment of AF by catheter ablation with pulmonary vein isolation (PVI) is considered as the cornerstone of treatment of AF[5]. Data published from many recent prospective multi-center clinical trials for ablation devices demonstrate that acute PVI is a reliable treatment in reducing long-term recurrence of PAF. The energy modality that has been most predominantly used for pulmonary vein isolation (PVI) has been radiofrequency (RF)[5]. RF ablation destroys cells through conductive and resistive tissue heating[36]. While highly efficacious, collateral damage and thermally induced injuries, such as esophageal fistula and PV stenosis, are rare but serious adverse events posed by the procedure[5].

Published animal and human studies demonstrate the potential for PFA to be a safe and efficacious way to deliver energy for pulmonary vein isolation via a non-thermal ablative modality [37, 38]. PFA has an additional benefit of being tissue selective, which reduces risk of collateral tissue injury. PFA energy can be applied selectively to cardiac cells, while preserving surrounding tissue [37].

The BWI IRE Ablation System provides a novel approach for the treatment of cardiac arrhythmias by using pulsed electrical field (PEF) energy to produce targeted intracardiac lesions and achieve the intended therapeutic effect. The VARIPULSE™ catheter is intended to allow for the ablation of larger areas of

tissue compared to traditional single tip catheters. This allows for shorter operator learning curves, faster total procedure times by creating a circumferential contiguous lesion in the pulmonary vein, and also reduces the number of catheter exchanges.

[figure not shown]
CCI

CCI

CCI

[figure not shown]
CCI

[figure not shown]
CCI

CCI

CCI

CCI

[figure not shown]

Figure 9.1.1: The schematic of study design

Patients who sign the Informed Consent Form (ICF) will be treated with the VARIPULSE™ Catheter and TRUPULSE™ Generator. Study subjects will be followed for 12 months after the study index procedure. Up to 40 sites in the United States will participate in this study.

The study consists of two sequential phases, a Pilot Phase and a Pivotal Phase.

9.1.1 Pilot Phase

The pilot phase will enroll a total of 20 evaluable PAF subjects.

9.1.2 Pivotal Phase

The pivotal phase will consist of the roll-in and main phase.

The primary safety endpoint is the incidence of early onset PAEs (within seven (7) days of an ablation procedure which uses the VARIPULSE™ Catheter and TRUPULSE™ Generator per protocol, including the initial and repeat procedures). PAEs include the following AEs:

Atrio-Esophageal Fistula*	Phrenic Nerve Paralysis (permanent) ⁺
Cardiac Tamponade ^{**,***} /perforation ^{**}	Pulmonary Vein Stenosis ⁺⁺
Device or procedure related death ⁺⁺⁺	Stroke/CVA ^{†,††}
Major Vascular Access Complication/Bleeding	Thromboembolism
Myocardial Infarction	Transient Ischemic Attack (TIA)
Pericarditis	Pulmonary Edema (Respiratory Insufficiency)
Heart Block	Vagal Nerve Injury/ Gastroparesis

*Atrio-esophageal fistula occurring up to 90 days post AF ablation process procedure will be considered a PAE.

**Cardiac Tamponade/Perforation occurring up to 30 days post AF ablation process procedure will be considered a PAE

*** Hemodynamic compromise or instability is defined as Systolic BP < 80 mm Hg.

[†] Absent phrenic nerve function as assessed by a sniff test. Refer to Table 14.2.1.1 for permanent phrenic nerve paralysis definition.

⁺⁺ Pulmonary Vein Stenosis occurring anytime during the 12-month follow up period will be considered a PAE.

[†] Non-focal global encephalopathy requires unequivocal evidence based upon neuroimaging studies to be reported

^{††}

CCI

atrial tachyarrhythmia (AF, AT or AFL of unknown origin[†]) episodes based on electrocardiographic data (≥30 seconds on ECG or sponsor provided TTM or Holter device) during the effectiveness evaluation period (Day 91-Day 365 post index procedure) and freedom from the following failure modes:

- Acute procedural failure, including:
 - Failure to confirm entrance block in all pulmonary veins (except those that are silent and/or cannot be cannulated post-procedure) at the end of the procedure

[figure not shown]
Note: Subjects who have the study catheter inserted but do not undergo ablation with PFA energy delivery via the study catheter due to IRE system related reasons will be considered as acute effectiveness failures; subjects who are discontinued due to non-IRE system related reasons (e.g., pump, other equipment or anatomy that precludes treatment with the VARIPULSE™ catheter or a commercially available catheter) will not be considered as acute effectiveness failures.

- Repeat ablation failure, including:
 - More than 1 repeat ablation procedures for AF/AT/ AFL of unknown origin[†] during the 3-Month Blanking Period (Day 0-90 post index procedure).
 - Any repeat ablation procedure for AF/AT/ AFL of unknown origin during the evaluation period.

CCI

CCI

- AAD failure:
 - Taking a new AAD (Class I & III) for atrial tachyarrhythmia (AF, AT or AFL of unknown origin⁺) or taking a previously failed Class I/III AAD at a greater than the highest ineffective historical dose for AF/AFL/AT beyond the 3-month follow-up visit window (i.e., at any time from day 105-365 post index procedure).
- Continuous AF/AT/AFL of unknown origin⁺ on a standard 12-lead ECG during the effectiveness evaluation period.
- Any DC cardioversion procedure during the evaluation period for documented atrial tachyarrhythmia (AF, AT or AFL of unknown origin⁺) recurrences ascertained through protocol specified arrhythmia monitoring methods (12 lead ECG, TTM and Holter).

⁺AFL of unknown origin is defined as all AFL except those CTI dependent AFL as confirmed by 12-Lead ECG and entrainment maneuvers in an EP study.

9.2.3 Secondary Endpoints

The following hypothesis-driven secondary endpoints will also be evaluated.

9.2.3.1 Secondary Effectiveness endpoints:

- QOL Improvement:
 - Atrial Fibrillation Effect on Quality-of-Life Questionnaire (AFEQT): defined as improvement in total score at 12M post procedure compared to baseline score.

9.2.4 Additional Endpoints:

9.2.4.1 Safety Endpoints

- Incidence of Unanticipated Adverse Device Effects (UADEs)

- Incidence of Serious Adverse Events (SAEs) within 7 days (early onset), >7 to 30 days (peri-procedural) and >30 days (late onset) of initial ablation
- Incidence of bleeding complication (ISTH definitions): a) major bleeding, b) clinically relevant non-major bleeding and c) minor bleeding.

Refer to Section 14.2.2 for the definition of Serious Adverse Event. Refer to Appendix III: Study Definitions, for the ISTH bleeding complications definitions.

9.2.4.2 Effectiveness Endpoints

The following additional effectiveness endpoints will be assessed:

- Acute procedural success, defined as the percent of subjects with electrical isolation of all PVs with confirmed entrance block at the end of the procedure.
 - Acute reconnection identified by adenosine/isoproterenol challenge.
 - First pass isolation (achievement of entrance block after first encirclement evaluated prior to the 30-min waiting period and adenosine challenge)
 - Ablation by a non-study catheter for PVI (touch-up) among all clinically relevant targeted PVs and by subject
- Repeat ablation procedures
 - Timing (blanking period or after blanking)
 - % PV reconnection by targeted PV and by subject
 - Arrhythmia treated or non-PV targets
- Freedom from documented (symptomatic and asymptomatic) atrial tachyarrhythmia episodes based on electrocardiographic data (≥ 30 seconds on ECG or sponsor provided TTM or Holter device) during the effectiveness evaluation period (Day 91-Day 365) with the following criteria also deemed failure:
 - Taking any AAD (Class I or III) for AF beyond the 3-month follow-up visit window (i.e., at any time from day 105-365 post index procedure).
- 12 Month Single Procedure Treatment Success off AAD: The 12-month single procedure success is defined as freedom from documented symptomatic AF/AT/AFL (of unknown origin⁺) episodes based on electrocardiographic data (≥ 30 seconds on ECG or sponsor provided TTM or Holter device) through the effectiveness evaluation period following a single index ablation procedure with all other failure modes included:
 - Acute procedural failure
 - Non-study catheter failure, including:
 - use of a non-study catheter (NSC) to treat pulmonary vein targets/isolation of clinically relevant PVs (all PVs except those that are silent and/or cannot be cannulated) and left atrial non-PV AF targets during the index procedure.
 - AAD failure: Taking a new AAD (Class I & III) for atrial tachyarrhythmia (AF, AT or AFL of unknown origin⁺) or taking a previously failed Class I/III AAD, at a greater than the highest ineffective historical dose, for AF/AFL/AT beyond the 3-month follow-up visit window (i.e., at any time from day 105-365 post index procedure).

- Any DC cardioversion procedure during the evaluation period for documented atrial tachyarrhythmia (AF, AT or AFL of unknown origin[†]) recurrences ascertained through protocol specified arrhythmia monitoring methods (12-lead ECG, TTM and Holter).
- Clinical Success: defined as freedom from documented symptomatic atrial tachyarrhythmia episodes based on electrocardiographic data (≥ 30 seconds on ECG or sponsor provided TTM or Holter device) during the effectiveness evaluation period (Day 91-Day 365)
- QOL Improvement: Canadian Cardiovascular Society – Severity of Atrial Fibrillation (CCS-SAF): defined as improvement in scores of Class 0 to Class 4 at 12M post procedure compared to baseline scores of Class 0 to Class 4.
- Reduction in Cardiovascular hospitalization rates: defined as reduction in CV hospitalization 6M prior to enrollment compared to 12M post procedure
- Reduction in DC Cardioversion defined as number of DCCV 6M prior to enrollment compared to 12M post procedure
- AAD Utilization by timing: Defined as proportion of subjects on antiarrhythmic drugs by timing compared to baseline

[†]AFL of unknown origin is defined as all AFL except those CTI dependent AFL as confirmed by 12-Lead electrocardiogram (ECG) and entrainment maneuvers in an EP study

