10.2 Eligibility Criteria

Inclusion Criteria

Candidates for this study must meet ALL of the following criteria:

1. Symptomatic paroxysmal AF with:
 - a. At least two (2) symptomatic AF episodes within last six (6) months from enrollment
 - b. At least one (1) AF episode electrocardiographically documented within 12 months prior to enrollment. Electrocardiographic documentation may include, but is not limited to electrocardiogram (ECG); Transtelephonic monitoring (TTM), Holter monitor or telemetry strip, and
 - c. A physician's note indicating recurrent self-terminating AF within 7 days.
2. Failed at least one (1) AAD (Class I or Class III) as evidenced by recurrent symptomatic AF, intolerable side effects to the AAD, or contraindication to the AAD
3. Age 18-75 years
4. Willing and capable of providing consent
5. Able and willing to comply with all pre-, post- and follow-up testing and requirements.

Exclusion Criteria

Subjects will be excluded from the study if they meet ANY of the following criteria.

1. Previously diagnosed with persistent AF (> 7 days in duration)
2. AF secondary to electrolyte imbalance, thyroid disease, or reversible or non-cardiac cause (e.g., untreated documented obstructive sleep apnea and acute alcohol toxicity).
3. Previous surgical or catheter ablation for AF
4. Patients known to require ablation outside the PV ostia and outside the CTI region (e.g., atrioventricular reentrant tachycardia, atrioventricular nodal reentry tachycardia, atrial tachycardia, ventricular tachycardia and Wolff-Parkinson White)
5. Documented severe dilatation of the LA (LAD >50mm) antero-posterior diameter on imaging within 6 months prior to enrollment.
6. Documented LA thrombus by imaging within 48 hours of the procedure.

7. Documented severely compromised LVEF (LVEF <40%) by imaging within 6 months prior to enrollment
8. Uncontrolled heart failure or New York Heart Association (NYHA) Class III or IV
9. History of blood clotting, bleeding abnormalities or contraindication to anticoagulation (heparin, warfarin, or dabigatran),
10. Documented thromboembolic event (including TIA) within the past 12 months
11. Previous PCI/MI within the past 2 months
12. Coronary Artery Bypass Grafting (CABG) surgery within the past 6 months (180 days)
13. Valvular cardiac surgical/percutaneous procedure (i.e., ventriculotomy, atriotomy, valve repair or replacement and presence of a prosthetic valve).
14. Unstable angina within 6 months

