12.1 Antiarrhythmic Drugs

12.1.1 Definitions

- Antiarrhythmic drugs (AADs)

The study protocol will classify and analyze the following:

- Class I drugs (e.g., flecainide, propafenone, disopyramide, etc.)
 - Class III drugs (e.g., amiodarone, dronedarone, dofetilide, etc.)

- Previously Failed AAD

Any AAD that a subject has ever taken for the treatment of his/her AF, prior to enrollment, is considered a “previously failed AAD” if it meets both of the following conditions:

- prior to enrollment, the AAD was ineffective in controlling the subject’s AF or produced intolerable side effects leading to its discontinuation.
 - the AAD is administered for AF

- Contraindicated AAD

Any AAD contraindicated in the subject due to known medical conditions. The reason for contraindication MUST be documented for each subject

- New AAD

ANY AAD that was never taken for the treatment of AF prior to enrollment is considered a “new AAD” if the drug is administered to treat atrial tachyarrhythmia episodes post-enrollment.

Table 12.1.1.1 illustrates the corresponding status of primary effectiveness endpoints based on AAD therapy administered in the blanking and post-blanking periods.

Table 12.1.1.1: AAD Usage and Impact on Primary Effectiveness Classification

	Through Three-Month Follow-Up Visit Window (0-104 days post procedure)	Post-Three-Month Follow-Up Visit Window (105-365 days post procedure)
Class I and/or Class III AAD	Can be initiated, continued from prior to study enrollment, or increased in dose as long as the AAD is stopped on or before day 104 post procedure and subject will not be classified as a primary effectiveness failure.	If initiated a new AAD for atrial tachyarrhythmia (AF, AT or AFL of unknown origin ⁺) or taking a previously failed Class I/III AAD at a dose greater than the highest ineffective historical dose for AF/AFL/AT; subject will be classified as a primary effectiveness failure . Can be initiated, continued from blanking period, or increased in dose if drug is used NOT for the treatment of AF/AT/AFL of unknown origin ⁺ and subject will not be classified as a primary effectiveness failure. The reasons for use of Class I & III AAD other than AF are ventricular arrhythmias.

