8.4.3.2. Additional Effectiveness Endpoints

- **Acute procedural success:** Defined as the achievement of electrical isolation in all clinically relevant targeted PVs as evidenced by the confirmation of entrance block at the end of the index procedure. Use of a non-study catheter to achieve pulmonary vein isolation (PVI) due to an IRE-system malfunction is considered an acute procedural failure.
- **Acute reconnection:** Defined as the restoration of electrical conduction in any clinically relevant targeted PV as identified by adenosine/isoproterenol challenge during the index procedure.
- **First pass isolation (FPI):** Defined as the achievement of entrance block in all clinically relevant targeted PVs after first encirclement, evaluated prior to the adenosine challenge during the index procedure.
- **Touch-up by NSC:** Defined as the use of a NSC to achieve PVI in any clinically relevant targeted PV during the index procedure.

- **Repeat ablation procedures** for AF/AT/AFL of unknown origin during the 12-month follow-up period will be assessed. The evaluation will include the timing of repeat ablation (blanking period or evaluation period), any reconnections of PVs previously isolated during the index procedure, and the type of arrhythmia(s) treated during the repeat ablation, along with their corresponding targets.
- **Freedom from documented (symptomatic and asymptomatic) atrial tachyarrhythmia off Class I/III AAD:** Defined as freedom from documented (symptomatic and asymptomatic) atrial tachyarrhythmia episodes based on electrocardiographic data (≥ 30 seconds on ECG or sponsor provided CEM or Holter device) during the effectiveness evaluation period (Day 91-Day 365). Taking any Class I/III AAD for AF/AT/AFL of unknown origin beyond the 3-month visit window (i.e., any time from Day 105-365 post index procedure) will also be deemed a failure.
- **12 Month Single Procedure Treatment Success:** Defined as freedom from documented symptomatic atrial tachyarrhythmia episodes based on electrocardiographic data (≥ 30 seconds on ECG or sponsor provided CEM or Holter device) during the effectiveness evaluation period (Day 91-Day 365) following a single index ablation procedure with all other failure modes included.

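### The protocol's 'off AAD' single-procedure endpoint counts some subjects still on a previously failed Class I/III drug as successes, and the SAP keeps that rule under a different name

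*Protocol*

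**What the plan says.** The endpoint is one of the additional effectiveness endpoints in Protocol 9.2.4.2. Its definition begins "12 Month Single Procedure Treatment Success off AAD: The 12-month single procedure success is defined as freedom from documented symptomatic" arrhythmia and then lists further failure modes. The drug failure mode has two limbs: a new Class I/III AAD, or "taking a previously failed Class I/III AAD, at a greater than the highest ineffective historical dose, for AF/AFL/AT beyond the 3-month follow-up visit window", which the protocol sets as Day 105 to 365. Nothing is said against a previously failed drug at or below the threshold dose.

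The endpoint just before it in the same section uses a different rule. There, "Taking any AAD (Class I or III) for AF beyond the 3-month follow-up visit window" is a failure, with no dose condition.

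The AAD table in Protocol 12.1.1, written for the primary endpoint, has the same threshold in its Day 105-365 column: "taking a previously failed Class I/III AAD at a dose greater than the highest ineffective historical dose for AF/AFL/AT". Its Day 0-104 column allows use without failure "as long as the AAD is stopped on or before day 104 post procedure".

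SAP 8.4.3.2 names the single-procedure endpoint without 'off AAD' and defines success "following a single index ablation procedure with all other failure modes included". The AAD failure mode this brings in (SAP 8.4.1.2) has the same dose threshold. The SAP gives an 'off Class I/III AAD' label to a separate endpoint, in which "Taking any Class I/III AAD for AF/AT/AFL of unknown origin beyond the 3-month visit window" is a failure. SAP 8.4.3 states that additional endpoints carry no formal test.

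**The concern.** A reader takes a rate labelled single-procedure success off AAD to describe subjects who stayed free of arrhythmia after one ablation without membrane-active drugs. The definition beneath that label is the primary endpoint's drug rule, which deliberately tolerates some continued drug use. That tolerance may be reasonable for the primary endpoint, but it does not match the words 'off AAD'.

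The gap is not empty by construction. Every subject enters under a criterion that reads "Failed at least one (1) AAD (Class I or Class III) as evidenced by recurrent symptomatic AF", or intolerance or contraindication, so many will have a previously failed drug on record. The post-procedure guidelines in Protocol 12.1.1 require a drug to be stopped before Day 104 if it was not prescribed for recurrence, so they leave room for use beyond that day when it was. At stake is whether the trial can state an off-drug single-procedure result at all, and whether protocol and report use one name for one quantity.

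**Working it through.** No sample size, power or stated rate belongs to this endpoint, so there is no plan figure to reproduce. The check is a classification, followed by an illustration of size.

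**Step 1. Classify a subject with no other failure**, by Class I/III use for AF/AT/AFL on Day 105-365:

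| Drug use | Protocol 'off AAD' rule (same rule in the SAP) | Any-Class I/III rule |
|---|---|---|
| None | success | success |
| Previously failed, at or below threshold dose | **success** | failure |
| Previously failed, above threshold dose | failure | failure |
| New drug | failure | failure |

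The rules differ in one row only. Every success under the any-drug rule is also a success under the current rule, so the current proportion cannot be the lower of the two.

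**Step 2. Does the Day 104 wording close that row?** No. The stopping condition sits in the Day 0-104 column of a table about the primary endpoint. The Day 105-365 column, which governs the later period, fails only a new drug or a dose above the threshold. Protocol 9.2.4.2 itself contains no stopping condition.

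**Step 3. Does another visible analysis supply the result?** The SAP's separate 'off Class I/III AAD' endpoint lists no acute procedural failure, repeat-ablation failure or non-study-catheter failure. A subject who was re-ablated or touched up with another catheter, and then stayed free of arrhythmia and drug, would be a success, so it is not a single-procedure rate. It also counts asymptomatic episodes, which the single-procedure endpoint does not. AAD utilization is summarised by timing, but its visible text does not cross drug use with success.

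**Step 4. Size.** Let S be the success rate as defined, and f the share of all subjects counted as successes while on a previously failed Class I/III AAD at or below the threshold dose. Then

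off-drug rate = S − f, and overstatement = f.

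Neither S nor f is in the documents. Assume S = 70%, with n = 225 evaluable subjects (SAP section 7):

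| f (assumed) | Off-drug successes | Off-drug rate | Overstatement |
|---|---|---|---|
| 0% | 0.70 × 225 = 157.5, about 158 | 70% | 0 points |
| 2% | 0.68 × 225 = 153 | 68% | 2 points |
| 5% | 0.65 × 225 = 146.25, about 146 | 65% | 5 points |
| 10% | 0.60 × 225 = 135 | 60% | 10 points |

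The choice of S does not affect the overstatement. The identity is exact for a simple proportion. SAP 8.13.2 uses Kaplan-Meier estimates, for which the gap also depends on censoring and on when the drug use occurs.

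**The case against.** The strongest reply is that the SAP has already dealt with the label. It drops 'off AAD' from the single-procedure endpoint and keeps an off-drug label for an endpoint that really does fail any such drug taken for AF/AT/AFL. A reader might infer that the trial will publish an inflated off-drug rate. The documents do not support that, because a report following SAP names would not call this rate off-drug. This part stands and limits the point to a conflict between the documents and a missing analysis.

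It is also fair that the endpoint is descriptive, that study success rests on the two primary endpoints alone (SAP 8.5.3), and that use of a drug previously not tolerated or contraindicated is a major deviation under Protocol 12.1.1, which narrows the group concerned. The tolerated dose is, by definition, one that was ineffective before, so it should not be asserted that drug is suppressing rhythm in these subjects. They are simply not off drug.

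Two further inferences are tempting and should be resisted. One is that no planned analysis anywhere gives the off-drug result. SAP 8.9 on exploratory analyses is wholly redacted, as is part of the AAD-utilization text, so the statement can cover visible text only. The other is that drug use for any indication ought to be a failure. Protocol 12.1.1 confines other reasons for Class I/III use to ventricular arrhythmias. Failing those subjects would be a different estimand, open to debate, and not the correction of an error.

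What the reply does not remove is the mismatch in Protocol 9.2.4.2 between a label and the rule beneath it, a few lines after the protocol shows how it words a true off-drug rule.

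**Conclusion.** The point holds in this form. The protocol's 'off AAD' single-procedure endpoint includes as successes subjects taking a previously failed Class I/III AAD for AF/AT/AFL at or below the highest ineffective historical dose on Day 105-365. It does not extend to doses above that threshold or to new drugs, both of which are failures. The SAP changes the name without changing the rule, so one quantity has two names, and the result the protocol names is not delivered by any unredacted analysis.

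The direction is known for a proportion: equal to or above the off-drug rate. The size is not known. The 2 to 10 points shown follow one for one from an assumed share of 2% to 10%, and no particular figure should be reported as a finding. There is no effect on alpha, power, the primary endpoints or the criteria for study success.

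**What to change.** In Protocol 9.2.4.2 and SAP 8.4.3.2 and 8.13.2, define the endpoint labelled 'off AAD' so that any Class I/III AAD taken for AF/AT/AFL of unknown origin on Day 105-365, at any dose, is a failure. Keep the indication qualifier and leave the other failure modes as they are. Report the current SAP version beside it under a name that states its rule, for example 'single-procedure success, primary-endpoint AAD rule'. A label such as 'on or off AAD' would be wrong, because that version still fails new drugs and higher doses. Use the same two names in both documents.

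The cost is one extra derivation and a possibly lower off-AAD rate. No new data are needed: Protocol 13.5 already collects cardiac medication names, indications, and start and end dates, and an any-dose rule needs no dose comparison. This changes only how the endpoint is classified and labelled. It implies nothing about how subjects should be treated.
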